9.3 POPULATIONS FOR ANALYSES

The following populations are defined ([Table 6](#)):

Table 6 - Populations for analyses

Population	Description
Screened	All participants who sign the ICF/assent form
Randomized	The randomized population includes all participants with a treatment kit number allocated and recorded in the IRT database, and regardless of whether the treatment kit was used or not. Participants treated without being randomized will not be considered randomized and will not be included in any efficacy population.
Intent-to-treat (ITT)	All randomized participants analyzed according to the treatment group allocated by randomization regardless if treatment kit is used or not.
Safety	All participants randomly assigned to study intervention and who take at least 1 dose of study intervention. Participants will be analyzed according to the intervention they actually received. Randomized participants for whom it is unclear whether they took the study medication will be included in the safety population as randomized. For participants who accidentally receive different treatment from the planned, the actual intervention allocation for as-treated analysis will be the dupilumab group.

Population	Description
Pharmacokinetic (PK)	The PK population includes all participants in the safety population with at least 1 non-missing result for functional dupilumab concentration in serum after first dose of the study treatment. Participants will be analyzed according to the intervention actually received.
Anti-drug antibody (ADA)	ADA population includes all participants in the safety population who have at least 1 non-missing result in the ADA assay after the first dose of the study treatment. Participants will be analyzed according to the intervention actually received.

ADA: antidrug antibody; ICF: informed consent form; IRT: interactive response technology; ITT: intent-to-treat; PK: pharmacokinetic

Endpoints not required for children aged ≥ 6 to < 12 years will be analyzed using the ITT population in adults and adolescents (≥ 12 to < 18 years).

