3 STATISTICAL ANALYSES

3.1 GENERAL CONSIDERATIONS

All comparisons will be of dupilumab (300 mg q2w for adults and adolescents/children ≥ 60 kg at screening, or 200 mg q2w for adolescents/children ≥ 30 kg and < 60 kg at screening, or 300 mg q4w for adolescents/children ≥ 15 kg and < 30 kg at screening) versus placebo.

A multiplicity-controlled hierarchical approach is proposed to control the overall type-I error rate for testing the primary and selected secondary efficacy endpoints at an alpha of 0.05. The study is considered positive when the primary endpoint achieves statistical significance with 2-sided significance level 0.05.

In general, continuous data will be summarized using the number of observations available, mean, standard deviation (SD), median, Q1, Q3, minimum, and maximum. Categorical data will be summarized using the count and percentage of participants.

The baseline value is generally defined as the last available value before the first dose of double-blind investigational medicinal product (IMP). For participants randomized but not treated, the baseline value is defined as the last available value before randomization.

For endpoints collected on the daily Nasal Symptom Diary, if there are 4 or more measurements collected within 7 days prior to the first dose of double-blind IMP (or prior to randomization for participants randomized but not treated), baseline is defined as the average of the scores in the 7 days prior to the first dose of double-blind IMP (or prior to randomization for participants randomized but not treated); if less than 4 measurements are collected, the baseline will be the average of the most recent 4 measurements prior to the first dose of double-blind IMP (or prior to randomization for participants randomized but not treated).

Stratification factors used in analyses will be derived based on eCRF data (for age, time from last surgery and country) and central-reading nasal endoscopy data (for disease pattern).

Unless otherwise specified, analyses will be performed by intervention group and overall for baseline and demographics characteristics.

Observation period

The observation period will be divided into 4 segments:

- The **pre-treatment period** is defined as the period up to first investigational medicinal product (IMP) administration.

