Each of the imputed complete data will be analyzed by fitting an ANCOVA model as described above. Statistical inference obtained from all imputed data will be combined using Rubin's rule. Descriptive statistics including number of participants, mean, standard error, and least squares (LS) mean changes (and standard error) will be provided. In addition, difference of the dupilumab group against placebo in LS means and the corresponding 95% confidence intervals (CI) will be provided along with the p-value.

A separate summary of primary endpoint will be provided for pediatric patients.

The multiple imputation and analysis model for the primary analysis of change from baseline in LMK values will be built with the following sample SAS code.

1. 40 datasets with a monotone missing pattern will be obtained, induced by Markov Chain Monte Carlo (MCMC) method on all participants excluding participants who undergo/plan to undergo surgery for AFRS or take SCS for any reason on or before Week 52.

```
proc mi data=ads out=monotone n impute=40 seed=16724;
  where wocfl='N';
  var time region trt01p value0 value24 value52;
  mcmc chain=multiple impute=monotone;
run;
```

2. For each of the imputed datasets with monotone missing pattern in step 1, the remaining missing data at baseline and post-baseline visits will be imputed using regression method for the monotone missing pattern with adjustment for covariates including time from last surgery (≤ 2 years, > 2 years), region (Americas, Asia) and intervention group.

```
proc mi data=monotone out=dat_mi nimpute=1 seed=16724 minimum=... 0 0 0  
maximum=... 24 24 24; /*LMK score range is 0-24*/
```

```
    by _imputation_;  
    class time region trt01p;  
    var time region trt01p value0 value24 value52;  
    monotone reg (/details);  
run;
```

3. Each of the 40 imputed datasets will be merged with one dataset imputed by WOCF approach, and then be analyzed using the main statistical model. These 40 imputed datasets will be saved.

```
%macro w1;  
    %do i=1%to 40;  
        data wocf&i.;  
        set ads;  
        where wocffl='Y';  
        _imputation_=&i.;  
        run;  
    %end;  
    data wocf_all;  
        set %do j=1 %to 40; wocf&j. %end;;  
        run;  
    %mend w1;  
  
%w1;  
  
data mi;  
    set dat_mi wocf_all;  
run;  
  
proc sort data=mi; by _imputation_; run;  
  
proc glm data=mi;  
    by _imputation_;  
    class time region trt01p;  
    model change=time region trt01p value0;  

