    lsmeans trt01p / stderr;  
    estimate 'Diff dupilumab vs placebo' trt01p -1 1;  
    ods output LSMeans=lsmeans Estimates=estimates;  
run;
```

4. Applying Rubin's rules to combine analysis results (point estimates and standard errors) from 40 imputations using PROC MIANALYZE for the LS means and difference in LS means between dupilumab and placebo.

```
proc sort data=lsmeans; by trt01p _imputation_; run;  
  
proc mianalyze data=lsmeans;  
    by trt01p;  
    modeleffects lsmean;  
    stderr stderr;  
    ods output ParameterEstimates=lsmean;  
run;  
  
proc mianalyze data=estimates;  
    modeleffects estimate;  
    stderr stderr;  
    ods output ParameterEstimates=lsmeandiff;  
run;
```

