3.3.1.2 Main analytical approach

Continuous secondary efficacy endpoints

Continuous secondary efficacy endpoints will be analyzed similarly as primary estimand of primary endpoint.

[figure not shown]
Percent change from baseline in total IgE in serum at Week 52

[figure not shown]
This secondary endpoint will be analyzed similarly as primary estimand of primary endpoint, and will be performed on safety population.

[figure not shown]
Proportion of participants who receive SCS and/or undergo/plan to undergo surgery for AFRS during the planned study treatment period

[figure not shown]
This secondary endpoint will be analyzed with the primary estimand defined according to the following attributes:

[figure not shown]
- Endpoint: Proportion of participants who receive SCS and/or undergo/plan to undergo surgery for AFRS during the planned study treatment period
- Treatment condition: dupilumab will be compared to placebo
- Analysis population: ITT population
- Intercurrent events (IE):
 - The following IEs will be handled with a treatment policy strategy:
 - Discontinuation of study intervention
 - Taking antifungals or other prohibited/rescue medications
- Population-level summary
 - After the implementation of IE handling strategy,
 - Missing data handling: Participant who discontinue the study prior to Week 52 without an event will be considered as no event.
 - Risk difference between interventions as well as the corresponding 95% confidence interval (CI) will be estimated using Mantel-Haenszel estimate and confidence limits, with Mantel-Haenszel stratum weights for time from last surgery (≤ 2 years, > 2 years) and region (Americas, Asia) and the Sato variance estimator. The P-value associated with Mantel-Haenszel method will be provided.
 - Descriptive statistics including number and proportion of participants with events will be provided for each intervention group.

[figure not shown]

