3.5 MULTIPLICITY ISSUES

The multiplicity procedure is proposed to control the overall type-I error rate for testing the primary and selected secondary endpoints. The overall alpha is 0.05. The comparisons with placebo will be tested based on the hierarchical order below at 2-sided $\alpha = 0.05$:

- Change from baseline in sinus opacifications assessed by CT scans using LMK score at Week 52
- Change from baseline in monthly average nasal congestion/obstruction score from the Nasal Symptom Diary at Week 24
- Change from baseline in endoscopy NPS at Week 24
- Change from baseline in sinus opacifications assessed by CT scans using LMK score at Week 24
- Change from baseline in monthly average TSS derived from the Nasal Symptom Diary at Week 24
- Change from baseline in UPSIT at Week 24
- Change from baseline in the score of decreased/loss of smell using the Nasal Symptom Diary at Week 24
- Change from baseline in endoscopy NPS at Week 52
- Change from baseline in monthly average nasal congestion/obstruction score from the Nasal Symptom Diary at Week 52
- Change from baseline in SNOT-22 total score at Week 52
- Change from baseline to Week 52 in three-dimensional CT total volume occupied by disease in all sinuses (%)
- Proportion of participants who receive SCS and/or undergo/plan to undergo surgery for AFRS during the planned study treatment period
- Change from baseline in SNOT-22 total score at Week 24
- Percent change from baseline in total IgE in serum at Week 52

The study is considered positive when the primary endpoint achieves statistical significance with 2-sided significance level 0.05.

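### The SAP's pooling code supplies no complete-data degrees of freedom, so a 62-participant ANCOVA is tested against a near-normal reference: type-I error about 5.2-5.7% instead of 5%, and 95% CIs up to about 3% too narrow

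*SAP*

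**What the plan says.** SAP 3.1 undertakes to "control the overall type-I error rate for testing the primary and selected secondary efficacy endpoints at an alpha of 0.05", two-sided. SAP 3.2.2 plans 40 imputations, and the prose states: "Each of the imputed complete data will be analyzed by fitting an ANCOVA model as described above". The results are then combined by Rubin's rule. Protocol 9.4.2 names the same rule. Neither document gives a complete-data df or a small-sample adjustment.

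The SAP says the primary analysis will be built with the sample code that follows. Three parts of it matter here:

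- Step 3 fits "model change=time region trt01p value0" by PROC GLM in each imputed dataset.
- Step 3 also states: "Each of the 40 imputed datasets will be merged with one dataset imputed by WOCF approach".
- Step 4 pools twice, once for the LS means and once for the treatment difference ("proc mianalyze data=estimates"). Each call names an estimate and its standard error and nothing else.

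SAP 3.3.1.2 extends the approach to the continuous secondary efficacy endpoints. For total IgE it says: "This secondary endpoint will be analyzed similarly as primary estimand of primary endpoint, and will be performed on safety population". Under Protocol 9.3, endpoints not required for children under 12 "will be analyzed using the ITT population in adults and adolescents". SAP 3.5 lists 14 tests: "The comparisons with placebo will be tested based on the hierarchical order below".

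**The concern.** A pooling step that receives only estimates and standard errors cannot know that the trial has 62 participants. Unless the complete-data df are supplied, it behaves as if they were infinite. The less data are missing, the closer the reference comes to the normal. With no missing data the pooled p-value would not reproduce the t-test with 57 df that PROC GLM gives for the same model.

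The error runs in the anti-conservative direction. It affects p-values and CIs for the primary endpoint and for the 12 other continuous endpoints in the hierarchy; the rescue-therapy proportion, analysed by the Mantel-Haenszel method, is the exception. A secondary endpoint with a borderline result could pass and open the next step when it should not.

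A related gap in the code: the model's outcome is `change`, but no step shown recomputes it once the Week 52 value has been imputed. If `change` is missing in the input dataset for those participants, PROC GLM would drop them. The prose requires the completed datasets to be analysed, so this is a step missing from the code and not a different planned analysis.

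**Working it through.** **Inputs**

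- About 62 participants, 1:1 (SAP 1.1).
- m = 40 imputations (SAP 3.2.2).
- ANCOVA parameters: intercept, time from last surgery, region, treatment and baseline, 5 in all (SAP 3.2.2, step 3).
- Two-sided alpha 0.05 (SAP 3.5).
- Not in the documents: the amount of missing data, so a range is shown; and the procedure's default, assumed to be infinite complete-data df when `EDF=` is omitted.

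**No missing data**

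Error df = 62 - 5 = 57.

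- Correct reference: t(0.975, 57) = 2.0025, which gives the planned size of 5.00%.
- As coded: critical value 1.9600, so size = P(|t57| > 1.960) = 5.49%.
- CI half-width: 1 - 1.9600/2.0025 = 2.1% too short.

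**With missing data, by formula**

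Let r be the relative increase in variance due to missing data.

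- As coded: df = (m - 1)(1 + 1/r)². At r = 0.05 this is 39 × 21² = 17,199.
- With `EDF=57`: observed-data df = 57 × (58/60)/(1 + r). At r = 0.05 this is 55.1/1.05 = 52.5. Combining, 1/(1/17,199 + 1/52.5) = 52.3.

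| r | df as coded | small-sample df | size as coded | CI too short by |
|---|---|---|---|---|
| 0.01 | 397,839 | 54.5 | 5.51% | 2.2% |
| 0.05 | 17,199 | 52.3 | 5.53% | 2.3% |
| 0.10 | 4,719 | 49.6 | 5.56% | 2.4% |
| 0.30 | 732 | 40.1 | 5.66% | 2.9% |

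The last two columns take the small-sample df as the truth. For an endpoint analysed in fewer participants, say 50 (an assumption), error df = 45, and with no missing data the size is 5.62% and the CI is 2.7% too short.

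**By simulation under the null**

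Normal data, n = 62, m = 40, 60,000 trials per setting, Monte Carlo SE 0.09 percentage points:

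| Missing at Week 52 | as coded | with `EDF=57` |
|---|---|---|
| 0% | 5.54% | 5.02% |
| 5% | 5.40% | 4.89% |
| 10% | 5.37% | 4.78% |
| 20% | 5.24% | 4.61% |

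Mean r was 0.05, 0.10 and 0.24 at 5, 10 and 20% missing.

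A second simulation, with assumed LMK-like data and some WOCF values (Monte Carlo SE about 0.1-0.15 points), gave:

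| Missing | WOCF | as coded | with `EDF=57` |
|---|---|---|---|
| 0% | 0% | 5.4% | 5.0% |
| 0% | 30% | 5.7% | 5.1% |
| 5% | 20% | 5.3% | 4.8% |
| 10% | 20% | 5.3% | 4.7% |

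A further run at 20% missing gave 5.7% as coded and 5.1% with the adjustment.

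**Chance that a decision changes (no missing data)**

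The two methods disagree when 1.960 < |T| < 2.0025, that is, when the correct p-value lies between 0.050 and 0.055. From the noncentral t with 57 df, this probability is 1.2% at 80% power (noncentrality 2.85) and 0.11% at 99% power (noncentrality 4.36).

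**The case against.** The strongest case on the other side is that this is a refinement. The SAP pre-specifies Rubin's rule, the large-sample df belong to that rule, and text and code agree. That does not rescue the stated 5% level: with no missing data the procedure is a t57 statistic compared with a normal critical value.

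Other objections have some force:

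- **The CI figure depends on the yardstick.** Working back from the first set of simulated sizes, instead of taking the small-sample df as true, the shortfall is about 1.7%, 1.6% and 1.1% at 5, 10 and 20% missing. The formula values are better read as an upper range once data are missing.
- **The adjustment need not calibrate better when much is missing.** In the first simulation at 20% missing, the code as written misses 5% by 0.24 points and the adjusted version by 0.39 in the other direction. The further run at 20% favoured the adjustment, so this depends on the scenario. It bears on Week 24 LMK, because Protocol 8.1.1.1 does not require that scan in adolescents and children.
- **Only one call changes a promised result.** SAP 3.2.2 promises standard errors for the LS means and a CI and p-value for the difference. `EDF=` alters df, CI and p-value, but not the pooled estimate or its standard error.
- **The 80% power case is illustrative.** The 80% in SAP 3.9 refers to the rescue-therapy endpoint, which is not pooled this way. No power is given for the affected secondary endpoints.

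That the code is labelled as sample code carries little weight, since the SAP says the analysis will be built with it and no other text supplies the missing df.

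**Conclusion.** The point holds and should be corrected, but its effect is small. As written, tests and CIs for 13 of the 14 hierarchy endpoints use a near-normal reference. The size is 5.49% with no missing data and about 5.2-5.7% across the formula and simulations. The CIs are 2.1% too narrow with no missing data and, by formula, up to 2.9% too narrow at r = 0.30; measured against simulated size the shortfall with missing data is smaller.

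The excess does not accumulate over the fixed sequence. With stated power above 99%, the primary conclusion is unlikely to turn on it. What is at stake is correct p-values and CIs, and the occasional borderline secondary endpoint.

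The figures assume that all 62 participants are analysed, that errors are normal, and that the procedure takes infinite complete-data df by default. LMK is a bounded 0-24 score with WOCF values, so they are approximate.

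**What to change.** 1. Add `EDF=` to the PROC MIANALYZE call for the treatment difference, and to the LS-means call for consistency. Set it to the PROC GLM error df of that endpoint's own model: participants in the ANCOVA minus 5. This is 57 for the primary endpoint if all 62 are analysed, lower where children under 12 are not assessed, and based on the safety population for total IgE.
2. State in SAP 3.2.2 that pooled tests and CIs use the small-sample df adjustment.
3. Show the derivation of `change` on `dat_mi` only, before it is combined with `wocf_all`: Week 52 minus baseline for the primary endpoint, Week 24 minus baseline for Week 24 endpoints, and 100 × (Week 52 - baseline)/baseline for IgE. Leave `wocf_all` untouched so that WOCF-assigned values are not overwritten.

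The cost is one option in two calls, one derivation step and one sentence. CIs become about 2-3% wider, and with about 20% missing data the test may become slightly conservative (4.6% in one simulation). Fixing the df method before unblinding also avoids having to choose it afterwards.

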3.3 SECONDARY ENDPOINT(S) ANALYSIS

The secondary endpoints detailed in this section are secondary efficacy endpoints and selected secondary biomarker endpoint. Other secondary endpoints analyses are defined in [Section 3.6.2](#) (AE, SAE), [Section 3.7.1.1](#) (PK), [Section 3.7.1.2](#) (immunogenicity) and [Section 3.7.1.4](#) (biomarker).

3.3.1 Secondary endpoint(s)

The Secondary efficacy endpoints include:

- Change from baseline in sinus opacification assessed by CT scans using the LMK score at Week 24
- Proportion of participants who receive SCS and/or undergo/plan to undergo surgery for AFRS during the planned study treatment period
- Change from baseline in monthly average nasal congestion/obstruction score from the Nasal Symptom Diary at Week 24 and Week 52
- Change from baseline in the monthly average anterior/posterior rhinorrhea score from the Nasal Symptom Diary at Week 24 and Week 52
- Change from baseline in endoscopy nasal polyp score (NPS) at Week 24 and Week 52
- Change from baseline in 22-item sino-nasal outcome test (SNOT-22) total score at Week 24 and Week 52
- Change from baseline in monthly average total symptom score (TSS) derived from the Nasal Symptom Diary at Week 24 and Week 52
- Change from baseline in visual analog scale (VAS) rhinosinusitis at Week 24 and Week 52
- Change from baseline in University of Pennsylvania smell identification test (UPSIT) at Week 24 and Week 52
- Change from baseline in the score of decreased/loss of smell using the Nasal Symptom Diary at Week 24 and Week 52
- Change from baseline to Week 52 in three-Dimensional CT volumetric measurement of the paranasal sinuses

The selected secondary biomarker endpoint include:

- Percent change from baseline in total IgE in serum at Week 52

3.3.1.1 ***Definition of endpoint(s)***

Sinus opacification assessed by CT scans using the LMK score

Please see the relevant definition of LMK score in [Section 3.2.1](#).

Systemic corticosteroids use

Systemic corticosteroids use is defined as the use of SCS for rescue treatment of AFRS or for another reason, and will be captured by the Investigator (or designee) on the appropriate page(s) of the eCRF page and the date and dosing information (daily dose, duration, INN). The reason for SCS use will be also captured.

Surgery (actual or planned) for AFRS

For participants who undergo or plan to have surgery for AFRS, the reason (worsening signs and/or symptoms during the study), the expected and real surgery date, the type and outcome of surgery will be recorded in a specific eCRF page.

Nasal congestion/obstruction score from the Nasal Symptom Diary

Anterior/posterior rhinorrhea score from the Nasal Symptom Diary

Score of decreased/loss of smell using the Nasal Symptom Diary

Total symptom score (TSS) derived from the Nasal Symptom Diary

The Nasal Symptom Diary is designed to assess the severity of CRS nasal symptoms on a daily basis. These symptoms include nasal congestion/obstruction, loss of smell, anterior rhinorrhea and posterior rhinorrhea. Each of the individual items of the diary are scored with 0 ('No symptoms'), 1 ('Mild symptoms – symptoms clearly present, but minimal awareness and easily tolerated'), 2 ('Moderate symptoms – definite awareness of symptoms that is bothersome but tolerable'), or 3 ('Severe symptoms - symptoms that are hard to tolerate, cause interference with activities, or daily living'). Higher scores on the items of the individual symptoms denote greater symptom severity.

The TSS is a composite score (ranging between 0 and 9) consisting of the sum of the following symptoms assessed daily in the morning: nasal congestion/obstruction, decreased/loss of smell, rhinorrhea (average of anterior/posterior nasal discharge). Higher scores on the TSS indicate greater symptom severity.

Endoscopy nasal polyp score (NPS)

The endoscopy NPS allows the assessment of nasal polyp formation. Polyps on each side of the nose will be graded based on polyp size scores: 0 = no polyps; 1 = small polyps in the middle meatus not reaching below the inferior border of the middle turbinate; 2 = polyps reaching below the lower border of the middle turbinate; 3 = large polyps reaching the lower border of the inferior turbinate or polyps medial to the middle turbinate, 4 = large polyps causing complete obstruction. The total score is the sum of the right and left nostrils, ranging from 0 to 8.

22-item sino-nasal outcome test (SNOT-22) total score

The SNOT-22 is a PRO questionnaire designed to assess the impact of CRS on participants HRQoL. SNOT-22 has 22 items covering symptoms, social/emotional impact, productivity, and

sleep consequences of CRS. The recall period is past 2 weeks. Each item is rated on a 6-point Likert scale response option, ranging from 0 ('No problem') to 5 ('Problem as bad as it can be'). A global score ranging from 0 to 110 is calculated by summing the responses to all items; higher score indicates greater rhinosinusitis-related health burden.

Visual analog scale (VAS) rhinosinusitis

The rhinosinusitis VAS is used to evaluate the overall severity of rhinosinusitis. It is a recommended scale to determine the participant's disease severity, and to guide the treatment for CRS. The participant is asked to answer the following question: "How troublesome are your symptoms of your rhinosinusitis" by selecting a point on a 10-cm VAS from 0 ('not troublesome') to 10 ('worst thinkable troublesome'). Based on their score on the VAS, the severity of rhinosinusitis can be divided into 3 categories as follows:

- Mild = VAS 0 to 3
- Moderate = VAS >3 to 7
- Severe = VAS >7 to 10

University of Pennsylvania smell identification test (UPSIT)

The University of Pennsylvania smell identification test (UPSIT) (UPSIT 40 odorant test) is a rapid and easy-to-administer method to quantitatively assess human olfactory function. The test consists of 4 booklets, each containing 10 odorants with 1 odorant per page. Above each odorant strip is a multiple-choice question with 4 alternative words to describe the odor and the participant is asked to indicate which word best describes the odor. The score ranges from 0 to 40, with one point being awarded for each correctly identified odor, and 40 being the best possible score.

Three-Dimensional CT volumetric measurement of the paranasal sinuses

Three-dimensional volumetric measurement of the sinuses method is used to calculate:

- The volume of the air (mL)
- The volume of mucosa (mL)
- % occupied by disease
- Thickness of lateral wall

Each above test (the volume of the air, the volume of mucosa, % occupied by disease, and thickness of lateral wall), including location (ethmoid sinus, frontal sinus, maxillary sinus, and sphenoid sinus), laterality (right and left) and direction (anterior and posterior for ethmoid sinus) will be analyzed separately and as the mean of the left and right measurements. The total volume occupied by disease in all sinuses will also be analyzed.

